3.2 Sample Size Considerations

No formal sample size calculation was performed. Based on the design of the parent studies, it is estimated that up to 24 patients will be enrolled in this study.

3.3 Randomization

Randomization is not applicable to this study. All patients will be treated with ATYR1940 under identical dosing guidelines.

4.0 Study Endpoints and Covariates

4.1 Safety, Tolerability, and Immunogenicity Variables

4.1.1 Safety and Tolerability

The safety and tolerability of ATYR1940 will be evaluated based on the following variables:

- Treatment-emergent adverse events (AEs)
- Serious adverse events (SAEs)
- Clinical laboratory tests:
 - Hematology, serum chemistry, and urinalysis
 - Complement and tryptase
- Electrocardiogram (ECG) results
- Vital signs
- Physical and neurological examinations
- Pulmonary evaluations
 - Pulmonary function tests (PFTs)
 - Forced expiratory volume in 1 second (FEV₁)
 - Forced vital capacity (FVC)
 - FEV₁/FVC ratio
 - Total lung capacity
 - Diffusion capacity of carbon monoxide (DLCO)
 - Pulse oximetry
 - Oxygen saturation (SpO₂) measurements
 - SpO₂ measurements below 95%

4.1.2 Immunogenicity Variables

Immunogenicity will be evaluated based on the following variables:

- Anti-drug antibody (ADA) titers
- Jo-1 antibody (Ab) seroconversion

4.2 Pharmacodynamic Variables

4.2.1 Muscle Surveillance Magnetic Resonance Imaging (MRI)

Magnetic resonance imaging (MRI) will be performed during the study to evaluate changes in lower extremity muscle disease burden following treatment with ATYR1940. Patients without contraindications for MRI will undergo a lower extremity skeletal muscle surveillance MRI examination at Week 1, every 3 months (Week 12, 24, etc), and 12-Week post-treatment follow-up or early termination. Images will be reviewed and interpreted by a central reader. Central readers will perform the following:

- Review the surveillance scan of the lower extremity muscles
- Determine the short tau inversion recovery (STIR) positive muscles and indicate:
 - STIR signal status (Yes for baseline, and Yes/No for follow-up)
 - Side of the body (right or left)
 - Name of the muscle (various)
 - Region of the muscle (proximal, middle, or distal)
- Use T1 image scores from the STIR positive muscles to determine presence of fatty infiltration using the Fischer score for scoring:

Fischer Scale	Description
• Grade 0	Normal appearance
• Grade 1 (mild)	Presence of traces of increased signal intensity on the T1-weighted MR sequences
• Grade 2 (moderate)	Presence of increased T1-weighted signal intensity with beginning confluence in less than 50% of the muscle
• Grade 3 (severe)	Presence of increased T1-weighted signal intensity with beginning confluence in more than 50% of the muscle
• Grade 4	End-stage appearance; entire muscle replaced by increased density of connective tissue and fat
• NA	Not a STIR positive muscle

- Prioritize the STIR positive muscles found in the baseline scan for each patient based on both the STIR hyperintensity and Fischer score (must be 3 or less).

4.2.2 Manual Muscle Testing (MMT)

Muscle strength will be assessed using Manual Muscle Testing (MMT) at Week 1, every 3 months (Week 12, 24, etc), and 1-Week Post-treatment Follow-up. Muscles are to be tested in the order specified in Section 8.3.1.3 of the study protocol. The muscle groups to be tested are provided below and, with the exception of neck flexors and extensors, will be tested bilaterally (i.e., left and right side) so that there are two measurements for each muscle group. Both neck flexors and extensors will be tested once and the single result will be utilized for both right and left sides in calculation of overall score

- | | |
|----------------------|-------------------------|
| • Trapezius | • Ankle dorsiflexors |
| • Deltoid middle | • Neck flexors |
| • Biceps brachii | • Gluteus medius |
| • Wrist extensors | • Neck extensors |
| • Wrist flexors | • Gluteus maximus |
| • Iliopsoas | • Hamstrings |
| • Quadriceps femoris | • Ankle plantar flexors |

Results for each muscle tested will be graded using a modified Medical Research Council scale. Scores will be converted to 13-point scale as shown below. An overall total score will be calculated by summing all scores for a total possible score of 336. An overall total score will be calculated as long as 24 of the 28 individual scores are non-missing. An upper extremity score will be calculated by summing all scores from the upper area of the body (i.e., trapezius, deltoid middle, biceps brachii, wrist extensors, wrist flexors, neck flexors, and neck extensors). Additionally, a lower extremity score will be calculated by summing all scores from the lower area of the body (i.e., iliopsoas, quadriceps femoris, ankle dorsiflexors, gluteus medius, gluteus maximus, and ankle plantar flexors). A total possible score for the upper and lower scores will be 168. Upper or lower scores will be calculated if 12 of the 14 scores are non-missing. Grades used in the scoring of results are presented below:

Grade	Converted Score	Description
• 5	12	Normal strength
• 5-	11	Uncertain muscle weakness
• 4+	10	Inability to resist against maximal pressure throughout range of motion
• 4	9	Ability to resist against moderate pressure throughout range of motion
• 4-	8	Ability to resist against minimal pressure throughout range of motion
• 3+	7	Ability to move through full range of motion against gravity and to resist against minimal pressure through partial range of motion, then contraction breaks
• 3	6	Ability to move through full range of motion against gravity
• 3-	5	Ability to move through greater than one half range of motion against gravity
• 2+	4	Ability to move through less than one half range of motion against gravity
• 2	3	Ability to move through full range of motion with gravity eliminated
• 2-	2	Ability to move in any arc of motion with gravity eliminated
• 1	1	A flicker of movement is seen or felt in the muscle
• 0	0	No contraction palpable

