8.2 Missing Data Conventions

Rules for partial dates are provided in Appendices 2 and 3. These rules will apply to adverse events and medications. Missing values for other variables will not be imputed.

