9.7.2 Other Pharmacodynamic Variables

Numeric pharmacodynamic variables will be summarized using descriptive statistics for actual, CFB, and percent CFB values. Numeric variables include the following:

- MMT composite score – all muscle groups, upper extremity muscle groups, and lower extremity muscle groups

- Upper extremity muscle function using the Brooke scale
- Lower extremity muscle function using the Vignos scale
- INQoL domains and QoL score
- FSHD-HI: subscale and total scores (do not include the short form score)

Listings will be provided for all of the additional pharmacodynamic variables.

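### MMT sums are reported with items missing and no rescaling or common-item rule, so change from baseline can compare sums over different muscles

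*SAP*

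**What the plan says.** SAP 4.2.2 converts each MMT grade to a score from 0 to 12. Fourteen muscle groups are scored on two sides. For the total, "An overall total score will be calculated by summing all scores for a total possible score of 336". Completeness is handled by thresholds: "An overall total score will be calculated as long as 24 of the 28 individual scores are non-missing", and "Upper or lower scores will be calculated if 12 of the 14 scores are non-missing". The neck is a special case: "Both neck flexors and extensors will be tested once and the single result will be utilized for both right and left sides". At the bottom of the scale, a converted score of 0 is described as "No contraction palpable".

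On missing data, SAP 8.2 gives rules for partial dates of adverse events and medications, then adds: "Missing values for other variables will not be imputed". Protocol 9.2.3 likewise restricts analyses to observed data.

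SAP 6.0 defines change from baseline as the post-baseline value minus the baseline value. It does not require that a composite be built from the same items at both visits. SAP 9.7.2, whose list includes the MMT composites, says: "Numeric pharmacodynamic variables will be summarized using descriptive statistics for actual, CFB, and percent CFB values". The shell for Table 14.3.1 points back to 4.2.2 for scoring and adds nothing.

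**The concern.** A sum that may leave out items, with no adjustment, gives a missing item the same weight as grade 0. The thresholds in 4.2.2 show that the authors expected some items to be missing, yet nothing says how the sum should allow for them. Nor is prorating an unwritten convention of this SAP. For the INQoL, section 4.2.4 spells out the multipliers to use when some items are incomplete; the MMT section has no counterpart. A programmer following 4.2.2 would add up whatever is present.

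Change in skeletal muscle strength is one of the exploratory objectives, and MMT is the only strength measure, since the Brooke and Vignos scales grade function. A patient whose muscles have not changed could show a change in Table 14.3.1 only because a muscle was graded at one visit and not at the other. That table reports the number of patients but not the number of items behind each score, so the summary would not reveal it.

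**Working it through.** **Inputs (SAP 4.2.2):** 14 groups on 2 sides; item scores 0 to 12; thresholds 24 of 28 and 12 of 14; each neck test entered for both sides. **SAP 6.0:** change = post-baseline − baseline.

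**The plan's own maxima.**
- Total: 14 × 2 = 28 items; 28 × 12 = 336. This reproduces.
- Upper score: 7 groups × 2 = 14 items; 14 × 12 = 168. This reproduces.
- Lower score: the list names six groups and omits hamstrings. 6 × 2 = 12 items; 12 × 12 = 144, not 168. With hamstrings, 7 × 2 × 12 = 168.

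**Largest error per occurrence.**
- Total: 28 − 24 = 4 items may be missing; 4 × 12 = 48; 48/336 = 14.3%.
- Upper score: 14 − 12 = 2 items; 2 × 12 = 24; 24/168 = 14.3%.
- Lower score: the same 24 of 168 if hamstrings are included. With the list as printed, only 12 items exist, so the 12-item threshold allows none to be missing.

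**Unchanged patient, same grade in every muscle.** With k items missing at one visit, that visit's sum is (28 − k) × score.

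| Item score | k | Full sum | Sum with k missing | Change if missing only after baseline | Change if missing only at baseline |
|---|---|---|---|---|---|
| 12 (grade 5) | 4 | 336 | 288 | −48 (−14.3%) | +48 (+16.7%) |
| 9 (grade 4) | 4 | 252 | 216 | −36 (−14.3%) | +36 (+16.7%) |
| 6 (grade 3) | 4 | 168 | 144 | −24 (−14.3%) | +24 (+16.7%) |
| 9 (grade 4) | 2 (one neck test) | 252 | 234 | −18 (−7.1%) | +18 (+7.7%) |

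An item missing at both visits adds 0 to each sum and cancels in the absolute change. One missed neck test uses up the whole two-item allowance of the upper score, which would still be reported.

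**Effect on a group mean.** One unchanged grade-5 patient with four items missing after baseline moves the mean change by −48/24 = −2.0 points at the planned maximum of 24 patients. In a disease group of 8 (an assumed size) the shift is −48/8 = −6.0.

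**Candidate remedies, in unchanged patients with four items missing after baseline.** Prorated total = (sum of graded items / number graded) × 28.

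| Case | True total | Raw sum and change | Prorated total and change | Common-item change |
|---|---|---|---|---|
| All items equal, at 9 | 252 | 216; −36 | 252; 0 | 216 − 216 = 0 |
| Missing four at 12, other 24 at 6 | 48 + 144 = 192 | 144; −48 | 168; −24 | 144 − 144 = 0 |
| Missing four at 3, other 24 at 10 | 12 + 240 = 252 | 240; −12 | 280; +28 | 240 − 240 = 0 |

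Prorating works when the missing muscles resemble the rest. When weak muscles are the ones missing, it can err by more than the raw sum, and in the favourable direction. Only the common-item change is 0 in all three cases. The second row also shows that percent change can exceed 14.3%: −48/192 = −25.0%.

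**The case against.** The strongest reply is that the documents give little reason to expect many missing items. Protocol 8.4.1.3 provides alternative positions for weaker patients, and its Table 3 lists a gravity-eliminated position for all 14 groups. The scale runs down to no contraction, so a very weak muscle receives a grade and does not become missing. A reader might infer that missing items will accumulate as disease advances; neither document gives a missing-item rate or shows it rising. This stands, and the figures above are per occurrence only.

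A reader might also infer that the artefact swamps the change the study is meant to detect. No target change, expected decline or sample size calculation is stated. A one-step loss in one muscle is 1 point, but that is the scale's smallest unit, not a detection target.

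Nor does the SAP assign 0 to a missing item. The zero follows from summing without adjustment, alongside the no-imputation rules and the contrast with the INQoL. It is a literal reading of the rule, not a quoted instruction.

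Finally, MMT is exploratory and descriptive in a single-arm extension with no hypothesis testing, and safety, tolerability and immunogenicity are the main goal. Listing 16.2.19 shows each muscle's converted score, so a gap can be traced patient by patient. This limits the consequence but does not make the tabulated change correct.

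**Conclusion.** The point holds as a moderate issue. As written, 4.2.2 yields MMT totals and sub-scores whose change from baseline can reflect which muscles were graded, not how strong they were. The error per occurrence is at most 48 points for the total and 24 for the upper score, and 24 for the lower score only once hamstrings are included. These figures assume that the sum is taken literally over the graded items.

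Two stronger conclusions are tempting and unsupported. One is that the rule manufactures disease progression: the sign depends on the visit at which the item is missing. The other is that the SAP cannot stand without this correction: the frequency is unknown, the measure is exploratory, and the item-level listing allows tracing.

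**What to change.** - Keep the 24-of-28 and 12-of-14 thresholds. Compute MMT change and percent change from baseline (Table 14.3.1, Listing 16.2.19) only over items graded at both visits, and apply the thresholds to those common items.
- State this as an exception to the change-from-baseline definition in SAP 6.0.
- Where an actual-value total is shown with items missing, flag it or show a prorated value marked as such. Do not derive change from prorated totals.
- Restore hamstrings to the lower-extremity list, so that 14 items and 168 points hold.

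The cost is some SAP wording and a small programming change, with no new data. SAP 1.0 provides for tracked changes before database lock. There are three downsides. The displayed change may not equal the difference between the displayed totals, which needs a footnote. A real change in a muscle not graded at both visits is not captured. Some patients with different gaps at the two visits will fall below the threshold: for example, three items missing at baseline and three others later leave 28 − 6 = 22 common items, so no change would be reported for the total.

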8.3. Concomitant Medications

All medications and supplements the patient received after completion of the last visit in the parent study and all medications and supplements the patient receives during the course of the study are to be documented in the source documents and in the eCRF.

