8.4.1.3. Manual Muscle Testing

Muscle strength is to be formally assessed at the time points designated in [Table 1](#) by the Investigator or designee using consistent methodology and by the same individual at the study center at all scheduled visits, if feasible.

Muscles are to be tested in the order defined in [Table 2](#). Generally, for bilateral muscle testing, each muscle group is first tested on the right and then the left, prior to proceeding to the next muscle group. Some muscle groups are listed with anti-gravity testing, but for a weaker patient, these are to be tested in a side-lying or supine position, per [Table 3](#); the re-test for a weaker patient is indicated in italics. The ankle plantar flexors are first tested in prone, and then retested in standing for scoring purposes. Results will be graded using a modified Medical Research Council scale⁵⁴ (see [Table 4](#)).

Table 2: Manual Muscle Testing Order

Position / Muscle Group	Order of Testing
Sitting	
Trapezius (shoulder elevators)	1
Deltoid middle (shoulder abductors)	2
Biceps brachii (elbow flexors)	3
Wrist extensors (extensor carpi ulnaris/radialis)	4
Wrist flexors (flexor carpi radialis/ulnaris)	5
Iliopsoas (hip flexors)	6
Quadriceps femoris (knee extensors)	7
Ankle dorsiflexors (tibialis anterior)	8
Supine	
Neck flexors (scalenes, sternocleidomastoid)	9
Trapezius (gravity eliminated test if needed) -	
Deltoid middle (gravity eliminated test if needed) -	
Gluteus medius (gravity eliminated test if needed) -	

Sidelying (lying on left side-right muscles tested)	
Gluteus medius (hip abductors)	10
Iliopsoas (gravity eliminated test if needed) -	
Gluteus maximus (gravity eliminated test if needed) -	
Hamstrings (gravity eliminated test if needed) -	
Biceps brachii (gravity eliminated test if needed) -	
Neck flexors (gravity eliminated test if needed) -	
Neck extensors (gravity eliminated test if needed) -	
<hr/>	
Prone	
Neck extensors (longissimus, semispinalis, iliocostalis, splenius cervicis)	11
Gluteus maximus (hip extensors)	12
Hamstrings (knee flexors)	13
Ankle plantar flexors (initial test; gastrocnemius)	14
<hr/>	
Sidelying (lying on right side-left muscles tested)	
Gluteus medius (hip abductors)	15
Iliopsoas (gravity eliminated test if needed) -	
Quadriceps (gravity eliminated test if needed) -	
Gluteus maximus (gravity eliminated test if needed) -	

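### SAP 4.2.2 omits hamstrings from the lower-extremity MMT score: as listed it has 12 items and a maximum of 144, not the stated 14 and 168

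*SAP*

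**What the plan says.** SAP 4.2.2 lists 14 muscle groups, hamstrings among them. All are tested on both sides except the neck flexors and extensors, which are tested once. For these two, "the single result will be utilized for both right and left sides in calculation of overall score". Grades convert to a 0 to 12 score. The overall total has 28 scores and a maximum of 336, and needs at least 24 non-missing scores.

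Two regional scores follow, each with its muscles given in a list introduced by i.e. The upper list names seven groups: trapezius, deltoid, biceps, wrist extensors, wrist flexors, neck flexors and neck extensors. The lower list names six: "iliopsoas, quadriceps femoris, ankle dorsiflexors, gluteus medius, gluteus maximus, and ankle plantar flexors". For both scores the SAP then states: "A total possible score for the upper and lower scores will be 168". It adds: "Upper or lower scores will be calculated if 12 of the 14 scores are non-missing".

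On procedure it says: "Muscles are to be tested in the order specified in Section 8.3.1.3 of the study protocol". In the protocol, section 8.3 is "8.3. Concomitant Medications". The testing tables are in "8.4.1.3. Manual Muscle Testing", where Tables 2 and 3 both include hamstrings.

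**The concern.** The lower list does not produce the item count or the maximum that the SAP gives for it, and one tested muscle group belongs to no regional score.

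This section is the working specification. SAP 9.7.2 plans summaries of the lower-extremity score, Listing 16.2.19 shows it, and the programming note to Table 14.3.1 sends the programmer to 4.2.2 for the rule. No other place in the documents gives a lower-extremity list. Skeletal muscle strength is a named study objective and MMT a named muscle-effects endpoint.

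A programmer who codes the list would report a score that leaves out knee-flexor strength. If the threshold of 12 is coded with it, one untested lower muscle on one side removes the score for that visit. Percent change from baseline, also reported in Table 14.3.1, would use too small a denominator.

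**Working it through.** **Inputs.** Muscle groups and lists: SAP 4.2.2. Scores per group: 2, with each single neck result used for both sides. Maximum converted score per item: 12 (SAP 4.2.2 conversion table; Listing 16.2.19 gives the range as 0 to 12).

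**Formulas.** Items = 2 x groups. Maximum = 12 x items.

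| Score | Groups | Items | Maximum | Stated | Agrees? |
|---|---|---|---|---|---|
| Overall | 14 | 14 x 2 = 28 | 28 x 12 = 336 | 28; 336 | Yes |
| Upper | 7 | 7 x 2 = 14 | 14 x 12 = 168 | 14; 168 | Yes |
| Lower, as listed | 6 | 6 x 2 = 12 | 12 x 12 = 144 | 14; 168 | No |
| Lower, with hamstrings | 7 | 7 x 2 = 14 | 14 x 12 = 168 | 14; 168 | Yes |

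**Size of the gap.** 168 - 144 = 24 points, which is two items of 12; 24/168 = 14.3%. The regional maxima as listed sum to 168 + 144 = 312. With hamstrings they sum to 168 + 168 = 336, the overall maximum. Comparing the 14 tested groups with the two lists leaves hamstrings as the only group in neither.

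**Missing-item rule.** Overall, 24/28 = 85.7%; regional, 12/14 = 85.7%. The thresholds match only if the lower score has 14 items. As listed, 12 items with 12 required allows 12 - 12 = 0 missing, against 14 - 12 = 2 intended.

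**Can the neck rule explain the gap?** No. The lower list contains no neck muscle. Counting each neck result once would give 12 x 2 + 2 = 26 items and 312 overall, and 5 x 2 + 2 = 12 items and 144 for the upper score. Both contradict the stated figures. The exercise does show that the upper 14 and 168 need the double count, which the text states only for the overall score. Read literally, the two regional maxima would sum to 144 + 144 = 288.

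**Illustration** (assumption: every lower item at grade 4, converted score 9). The baseline score is 12 x 9 = 108 as listed and 14 x 9 = 126 with hamstrings.

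- Both hamstrings fall to grade 3 (9 to 6), a loss of 2 x 3 = 6 points. As listed the change is 0; with hamstrings it is -6, and 6/126 = 4.8%.
- The other 12 items each fall by 1 point. The change is -12 either way, but 12/108 = 11.1% as listed and 12/126 = 9.5% with hamstrings.

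**The case against.** The best case on the other side concerns weight, not arithmetic. The rule opens with a sum over the lower area of the body and then states 14 items and 168. A careful programmer would see that six groups cannot give those figures and would add hamstrings. How the score was actually programmed cannot be seen from the documents. The analysis is descriptive, with no hypothesis testing and an estimated maximum of 24 patients. The protocol endpoint is muscle strength by MMT, and the regional scores exist only in the SAP. Item scores are listed, so a reader could rebuild the correct score.

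Much of this stands as a limit on impact. The loss of missing-item tolerance happens only if both the list and the threshold of 12 are coded as written. The illustration rests on an assumed grade and a chosen pattern of decline. The neck wording is settled by the stated 14 and 168, and the wrong protocol reference is editorial.

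It does not remove the error. A list introduced by i.e. defines the set, the upper list given the same way is complete, and the table shell points the programmer here. A scoring rule should not rely on the programmer noticing that it contradicts itself.

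**Conclusion.** The lower-extremity list in SAP 4.2.2 is wrong and must be corrected. It yields 12 items and a maximum of 144 against the stated 14 and 168. This is certain, because it follows from counting the SAP's own lists. That the list is at fault, and not the totals, follows because adding hamstrings reconciles 14, 28, 168 and 336 at once. The effects on reported results are conditional on programming from the list as written.

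The overall total (28 items, 336) is sound. The consequence is confined to the lower-extremity score in Table 14.3.1 and Listing 16.2.19. No size is claimed for missing items, because the documents give no missingness rate. The need to correct rests on the hamstrings omission alone; the neck wording and the cross-reference are secondary.

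**What to change.** 1. Add hamstrings to the lower-extremity list in SAP 4.2.2, giving 7 groups, 14 items and a maximum of 168.
2. In the same edit, say that each single neck result counts for both sides in the upper score as well as in the overall score.
3. Change the protocol reference from 8.3.1.3 to 8.4.1.3.
4. As a clarification only, say whether a composite with permitted missing items is a raw or a prorated sum. SAP 8.2 and Protocol 9.2.3 imply a raw sum, in which an untested muscle adds 0, the same as a muscle with no palpable contraction. Confirming that would be enough; proration is an option, not a required correction.

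The cost is one word, one phrase, one section number and one sentence, with no new data and no change to the table shells. The SAP's document history shows that a dry run has taken place, so the existing derivation should be checked against the corrected list and rerun if it followed the list as written. The item-level converted scores needed for this are already planned in Listing 16.2.19.
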